5.5.1 Assay Methods

Concentrations of vemurafenib and cobimetinib will be determined in plasma using validated liquid chromatography tandem mass spectroscopy methods.

Table 10 Schedule of PK Sampling for Patients Previously Treated with Vemurafenib ^{a,b}

Day of Assessment	-1					1					2	8	14					15	16	17	C2 D1	C2D8	C3D8				
Time (hr)	0	2	4	6	8	0	0.5	1	2	4	6	0	0	0	0.5	1	2	4	6	8	0	0	0	0	0, 2hr post-dose	0	
Vemurafenib	x	x	x	x	x	x						x	x	x	x	x	x	x	x	x	x	x	x ^b	x ^b		x	x
Cobimetinib 14/14						x	x	x	x	x	x	x	x	x	x	x	x	x	x	x	x	x				x	x
Cobimetinib 21/7						x	x	x	x	x	x	x	x	x	x	x	x	x	x	x	x					x	x
Cobimetinib continuous						x	x	x	x	x	x	x	x	x	x	x	x	x	x	x	x					x	x

^a Vemurafenib plasma levels samples shall be collected on Days 16 and 17 of C1 only when cobimetinib is given on a 14/14 schedule.

^b Patients on cobimetinib monotherapy will undergo PK sampling based on their assigned cobimetinib dosing schedule.

Table 11 Schedule of PK Sampling for Patients Either Previously Treated (but without Prior Exposure to BRAF or MEK Inhibitor Therapy) or Previously Untreated for Locally Advanced/Unresectable or Metastatic Melanoma ^a

Day of Assessment	1						2	8	14						15	16	17	C2 D1	C2D8	C3D8	
Time (hr)	0	0.5	1	2	4	6	0	0	0	0.5	1	2	4	6	8	0	0	0	0	0, 2hr post-dose	0
Vemurafenib	x	x	x	x	x	x	x	x	x	x	x	x	x	x	x	x	x ^b	x ^b		x	x
Cobimetinib 14/14	x	x	x	x	x	x	x	x	x	x	x	x	x	x	x	x	x	x		x	x
Cobimetinib 21/7	x	x	x	x	x	x	x	x	x	x	x	x	x	x	x	x				x	x
Cobimetinib Continuous	x	x	x	x	x	x	x	x	x	x	x	x	x	x	x	x				x	x

^a Vemurafenib plasma levels samples shall be collected on Days 16 and 17 of C1 only when cobimetinib is given on a 14/14 schedule.

5.6 Exploratory Molecular Assessments (Biomarker Assessments)

Samples collected for PD and biomarker assessments will be analyzed with the objective of understanding mechanisms of action and pharmacodynamics and to identify biomarkers that are predictive of response to the vemurafenib and cobimetinib combination or to cobimetinib alone or to explain mechanisms of resistance. Additional markers might be measured in case a strong scientific rationale for these analyses develops.

Specimens for dynamic (non-inherited) and genetic (inherited) biomarker discovery and validation will be collected from all patients participating in the trial.

The total volume blood loss for plasma, serum, and whole blood biomarker assessments will be approximately 18 mL.

For all samples, dates of consent and specimen collection should be recorded on the eCRF. For sampling procedures, storage conditions and shipment instructions, see the Sample Handling and Logistics Manual.

5.6.1 Plasma Samples

Blood (two approximately 6.0-mL samples in EDTA) for plasma isolation will be obtained at baseline. These samples will be used for biomarker assays, which may include BRAF mutations and other candidate biomarkers (including somatic mutations of the tumor).

5.6.2 Whole Blood for Biomarker Analyses

A blood sample (approximately 6 mL in K3 EDTA) for biomarker analysis will be collected as described in the laboratory manual.

The following assessments may be performed on whole blood:

- Analysis of new mutations (not described so far) detected in tumor tissue in order to verify the somatic nature of this mutation
- Single nucleotide polymorphisms (SNPs) in case evidence develops that SNPs might be associated with safety, efficacy, or pharmacokinetics of vemurafenib

5.6.3 Tissue Samples

For all patients tumor biopsies of accessible tissue are required.

5.6.3.1 Tumor Tissue

A final biopsy is requested at the time of progression. A lesion with the greatest change in dimension based on interval evaluation should be excised at time of progressive disease. As stated above, the scheduling of this tumor biopsy should not interfere with the scheduling of the FDG-PET scan.

Tumor biopsies will be obtained from patients with accessible progressing tumors at baseline following the patient's consent to participate in the trial. Failure to obtain

sufficient tumor sample after making best efforts to biopsy the tumor will not be considered a protocol deviation. If a biopsy at progression was submitted to Roche from an antecedent vemurafenib study within 3 months of enrollment, no baseline biopsy is required. For previously untreated patients only, the diagnostic tumor specimen may be substituted as baseline tumor sample.

If archival tumor tissue was not collected during the previous trial, or was inadequate for testing, then archival tumor tissue (formalin-fixed paraffin-embedded archival block or 20 unstained slides) may also be requested. Fine needle aspiration (FNA) biopsies are not acceptable.

In addition to the biopsies noted above, patients will be required to provide tumor biopsies approximately 10–14 days after the start of dosing with vemurafenib and cobimetinib in Cycle 1. The patient must be taking cobimetinib at the time of the Day 10–14 biopsy.

Scheduling of the tumor biopsy should not interfere with the scheduling of the first, post-baseline FDG-PET scan. The FDG-PET scan should not occur within 1 week following a study-mandated biopsy unless the biopsy is obtained from a site that is not a region of interest on the FDG-PET. Ideally, tumor biopsies at screening and during Days 10 to 14 of Cycle 1 should be performed after the mandated PET scans.

See the guidance below regarding the logistics for tumor biopsy and FDG-PET scanning in the case of multiple or single lesions.

- Multiple lesions: The tumor biopsy will be obtained from a lesion other than the one of interest being scanned for FDG-PET and should be obtained 1–4 hours after study drug dosing in Week 2 of Cycle 1, either before or after the scan.
- Single lesion: For patients with only one lesion for both the FDG-PET and the tumor biopsy, the timing of the FDG-PET scan is more important and the biopsy should be obtained after the second FDG-PET scan. The second FDG-PET scan (performed 10 to 14 days after start of dosing with vemurafenib and cobimetinib in Cycle 1) will be completed first (approximately 1–4 hours after dosing) and the tumor biopsy will then be obtained.

Formalin-fixed tumor tissue embedded in paraffin blocks (FFPE biopsy) and, if feasible, fresh-frozen tumor tissue will be collected at baseline, between Days 10 and 14, and at disease progression. The biopsy at disease progression should be taken from an enlarging lesion. Biopsies at progression should be obtained within 3 days of study drug discontinuation (i.e., continue study treatment for several days beyond documentation of progression, if necessary, in order to coordinate the timing of biopsy to occur within 3 days of study drug discontinuation).

Biopsies will be collected and immediately transferred into provided vials filled with formalin. The biopsies will then be fixed for 24 ± 2 hours, transferred into 70% ethanol, and then (in ethanol) shipped to a central pathology laboratory for paraffin embedding. In cases where a reasonable-sized biopsy (e.g., excisional biopsy, 5-mm punch or more than

one 14-gauge core biopsy) can be collected with formalin fixation, every effort should also be made to collect a fresh-frozen biopsy.

Fresh-frozen tumor (baseline, between Days 10 and 14, and at disease progression) may be used for whole genome analysis; other techniques such as reverse phase protein array or mRNA quantitation may also be performed.

FFPE tumor from baseline and disease progression biopsies will be used to perform the following assessments:

- IHC for molecules known to be relevant for activity of the MAPK pathway (ERK and MEK protein phosphorylation)
- IHC for molecules potentially related to response/resistance including BRAF, CRAF, and PTEN
- BRAF mutations (including V600E) and other somatic mutations affecting PI3K, RAS, RAF, and ERK

The following assessments are planned using the FFPE biopsy taken under treatment (Days 10–14):

- IHC for molecules that are potential PD biomarkers for vemurafenib and cobimetinib (e.g., ERK and MEK phosphorylation).

5.6.3.2 Presumed or Suspected Squamous Cell Carcinoma, Second Primary Melanoma, and Normal Skin

Formalin-fixed tissue embedded in paraffin blocks will be collected from patients who develop lesions presumed or suspected to be SCC or second primary melanomas during screening, the treatment period, and during follow-up. Tumor blocks will be returned after biomarker analyses have been performed. Unstained slides are acceptable if, despite all efforts, tumor blocks cannot be sent. Biopsies of suspicious malignant lesions not thought to represent SCC or second primary melanoma may be submitted at the discretion of the investigator.

Normal skin punch biopsies will be obtained under local anesthesia from all patients who develop SCC. Skin biopsies should be collected at the time the SCC lesion is excised in an area of normal skin (with hair follicles present) to the level of subcutaneous tissue. These samples may be obtained by using a 3- to 4-mm punch biopsy device, which should not require suturing. The skin biopsies will be formalin fixed on site and will be shipped in 70% ethanol.

FFPE samples from paired biopsies of SCC (or suspicious neoplasms) and normal skin will be used to perform immunohistochemical analyses of pathway markers (pERK, pMEK, p53), as well as somatic mutation analyses (including mutations of RAS, RAF, CDKN2A, and p53).

5.6.4 Storage of Pharmacodynamic and Exploratory Biomarker Samples

All PD and exploratory biomarker samples (plasma and/or tissue) will be stored for up to 5 years after completion of the study. Patients will have the option to consent that samples remaining after the protocol-defined analyses can be stored up to 15 years in the RCR.

If the patient consents to long-term storage, the RCR specimens will be destroyed no later than 15 years after the final freeze of the respective clinical database unless regulatory authorities require that specimens be maintained for a longer period. The implementation and use of the RCR specimens is governed by the RCR policy to ensure the appropriate use of specimens. If no consent has been given for long-term storage, all samples will be destroyed no later than 5 years after the initial freeze of the respective clinical database unless regulatory authorities require that specimens be maintained for a longer period.

The specimens in RCR will also be made available for future biomarker research towards further understanding of vemurafenib and cobimetinib treatment of advanced metastatic melanoma, related diseases, and adverse events and for the development of potential associated diagnostic assays.

Plasma and tumor specimens will be single coded as for all other clinical samples (labeled and tracked using the patient's study identification number).

5.7 Patients Who Have Discontinued Study Drug

All patients who discontinue vemurafenib and cobimetinib or cobimetinib monotherapy treatments will be followed for survival. Survival status will be assessed every 12 weeks until withdrawal of consent, death, or loss to follow-up, whichever occurs first.

5.8 Dosing beyond Progression

Dosing beyond progression is not recommended. Only under special circumstances when it is felt that the patient may clinically benefit by continued therapy should dosing beyond progression be considered. If it is judged by the investigator, in consultation with the Sponsor, that it is in the best interest of the patient, the patient may continue dosing of both vemurafenib and cobimetinib at the current dose or on cobimetinib alone. All patients who continue cobimetinib monotherapy dosing beyond progression will be dosed at 60 mg daily on a 21/7 schedule and will continue to be followed in their previously assigned cohort. Patients, who prior to progression could only tolerate a dose of cobimetinib below 60 mg daily, may continue dosing at their previously tolerated dose and schedule.

Special circumstances can be defined by, for example, cystic lesions, mixed responses, and new brain metastases that are treatable during the study with stereotactic radiotherapy or surgery but that do not require whole brain radiotherapy. If brain metastases are to be treated with stereotactic radiotherapy/gamma knife, vemurafenib and cobimetinib should be held 1 day prior to the procedure and may resume 1 day after the procedure is completed.

Patients who receive study therapy beyond progression must continue to undergo study visits, laboratory assessments and safety assessments and tumor assessments as specified in Sections 5.3 and 5.4. Tumor assessment scans collected post-progression will not be sent to ICON and the tumor assessment forms in the eCRF does not need to be completed.

Patients who receive study therapy beyond progression may stop study therapy anytime the investigator judges that the patient is no longer benefiting from the study therapy. Patients are required to stop study therapy if continued disease progression is documented in subsequent tumor assessments.

6. INVESTIGATIONAL MEDICINAL PRODUCT

This is an open-label study. Assignment of patients to specific dose cohorts will be tracked manually by the Sponsor. Study drug assignment will be handled manually by the Sponsor.

6.1 Dose and Administration Schedule of Vemurafenib and Cobimetinib

Patients enrolled in a given cohort will receive vemurafenib and cobimetinib at a specified dose combination as described in Section 3. Vemurafenib will be dosed orally bid and cobimetinib will be dosed orally qd.

Patients in screening (written informed consent) for this study who were previously receiving 960 mg bid vemurafenib will be dose-reduced to 720 mg bid for 7–14 days prior to Cycle 1 Day 1 in Cohorts 1, 1A, 2, 2A, or 1C. Patients receiving 960 mg bid vemurafenib prior to screening initiation (written informed consent) and assigned to Cohorts 1B, 1D, 3, 4, or 5 will continue receiving 960 mg bid vemurafenib, assuming this dose has been adequately tolerated prior to starting the study. Patients in screening (written informed consent) for this study who are treatment naive to vemurafenib at the time of consent will only start vemurafenib on Cycle 1, Day 1 once they are deemed eligible for enrollment.

Vemurafenib will be dosed daily and cobimetinib will be dosed on a 14/14 schedule, a 21/7 schedule, or a continuous daily schedule in a 28-day cycle.

On study visit days, the daily doses of cobimetinib will be taken in the clinic after pre-dose assessments have been performed. After establishing patient eligibility for continued administration of study drugs, patients will be given a sufficient number of tablets and/or capsules to last until the next visit. In some cases, extra tablets and/or capsules may be dispensed if there is a reasonable possibility that the patient's next visit may be delayed (e.g., due to inclement weather or distance of patient's home from study center).

Cobimetinib should be taken at approximately the same time each day, preferably in the morning, and no later than 4 hours after the scheduled time. Each dose of cobimetinib should be taken with a glass of water.

For vemurafenib, patients will receive study medication bottles, each containing tablets that are 240 mg each. The number of tablets for the morning and evening dose will

depend on the cohort assignment, with at least 8 hours between doses. Each dose of vemurafenib should be taken with a glass of water. As soon as feasible after signing informed consent, patients previously treated with vemurafenib should continue vemurafenib treatment with study drug provided expressly for this particular study and discontinue their supply of drug derived either from their antecedent vemurafenib study or a pharmacy.

Both cobimetinib and vemurafenib will be taken at the same time in the morning.

On PK sample collection days, patients will be required to come into the clinic and have vemurafenib and cobimetinib administered as part of the scheduled study visit after pre-dose assessments have been performed. Vemurafenib and cobimetinib may be taken with or without food, including on PK sampling days.

Patients will be instructed as to the number and strength of the tablets and/or capsules to take according to their assigned dose cohort. The cobimetinib and vemurafenib tablets and/or capsules should never be chewed or opened.

If a dose is missed (not taken within 4 hours after the scheduled dosing time), the patient should resume dosing with the next scheduled dose. Missed or vomited doses will not be made up.

Patients will be asked to record the time and date they take each dose in a medication diary. Missed doses should be recorded in a patient diary. Patients will be instructed to bring all unused study medication and their medication diaries to each study visit for assessments of compliance.

The protocol requires a study evaluation to occur on Day 1 of every cycle but allows a period of ± 3 days. Patients on the 14/14 and 21/7 dosing schedule of cobimetinib are required to have the minimum number of days per cycle without cobimetinib dosing 14 and 7 days, respectively. Patients are still expected to return for PK blood draws according to the schedule outlined in [Table 10](#) and [Table 11](#). For example, if a patient on a 21/7 cobimetinib dosing schedule has a study evaluation 2 days earlier than the nominal study day, the patient cannot restart cobimetinib until he/she has had at least 7 days without cobimetinib dosing.

6.1.1 Vemurafenib and Cobimetinib Dose Modification

Dose modifications, interruptions, and delays of vemurafenib and/or cobimetinib study treatment during and after the DLT assessment window should be made on the basis of the guidelines provided in [Table 12](#). Recognizing that new knowledge will be acquired and unforeseen safety issues may arise in the course of the study, the guidelines are not exhaustive and do not represent the full spectrum of care or treatment options described. The dose modification guidelines are not intended to replace clinical judgment or dictate care of individual patients.

Table 12 Vemurafenib and Cobimetinib Dose Modification Guidelines

Adverse Event	Action

A) Rash/desquamation: Grade ≥ 3
	
a) The appearance of rash must be characterized as acneiform or non-acneiform.
 
b) Acneiform rash
 
 • Initiate supportive measures per site guidelines. • Delay cobimetinib dosing until Grade ≤ 2. • Vemurafenib dosing may continue when cobimetinib is interrupted. • Reduce cobimetinib by one dose level (e.g., 60 to 40 mg at assigned dosing schedule). If after restarting at reduced dose, the patient experiences skin toxicity grade ≥ 3, further reduce cobimetinib by another dose level (e.g., 40 to 20mg at assigned dosing schedule). Permanently discontinue cobimetinib if restarting after second dose reduction, the patient experiences skin toxicity grade ≥ 3. • If rash Grade ≥ 3 persists for >28 days despite adequate supportive care, cobimetinib may be resumed if in the investigator's judgement, the benefit-risk of treatment remains favorable. 
c) Non-acneiform, maculo-papular rash
 
 • Initiate supportive measures per site guidelines. • Delay vemurafenib dosing until Grade ≤ 2. • Cobimetinib dosing may continue when vemurafenib is interrupted. • For Grade 3 rash, reduce vemurafenib by one dose level (e.g., 960 to 720 mg or 720 to 480 mg). If after restarting at reduced dose, the patient experiences skin toxicity Grade ≥ 3, further reduce vemurafenib by 1 dose level. Permanently discontinue vemurafenib if restarting after second dose reduction, the patient experiences skin toxicity Grade ≥ 3. • For Grade 4 rash, reduce vemurafenib by two dose levels (e.g., 960 to 480 mg or 720 to 240 mg). Permanently discontinue vemurafenib if after restarting at reduced dose, the patient experiences skin toxicity Grade ≥ 3.

Table 12 Vemurafenib and Cobimetinib Dose Modification Guidelines (Cont.)

Adverse Event	Action

B) Photosensitivity: Grade ≥ 3
	
a) In cases of Grade 2 photosensitivity, treatment with vemurafenib and cobimetinib may be continued for up to 1 week with the initiation of supportive measures. If the photosensitivity does not resolve to Grade ≤ 1 during this time or if the photosensitivity worsens to Grade ≥ 3, then both vemurafenib and cobimetinib treatment must be interrupted until the photosensitivity resolves to a Grade ≤ 1. If this occurs within 28 days, treatment may be re-initiated with vemurafenib dose reduced by one level (e.g., 720 to 480 mg).
 
b) If the photosensitivity does not resolve to Grade ≤ 1 by 28 days, then the therapy with vemurafenib and cobimetinib should be discontinued.
 
c) If the photosensitivity recurs to Grade ≥ 3 with vemurafenib and cobimetinib, re-initiation despite prophylactic measures and the dose reduction of vemurafenib, then both agents should be held until the photosensitivity resolves to Grade ≤ 1 or less. Cobimetinib should be dose reduced by one level when treatment is re-initiated (e.g., 80 to 60 mg on a 14/14 day schedule; from 60 to 40 mg on a 21/7 or a continuous schedule). The dose of vemurafenib should be maintained at the previously reduced dose.
 
d) If photosensitivity recurs a second time to Grade ≥ 3 despite prophylactic measures and the aforementioned dose reductions of vemurafenib and cobimetinib, either one or both study treatments may resume if in the investigator’s judgement, the benefit-risk of treatment remains favorable.

C) New skin lesion, suggestive of SCC; SCC is considered a Grade 3 event in NCI CTCAE v4.0
	
a) Follow SCC Risk Management Plan detailed in protocol (Section 5.3.4.6)
 
b) Interrupt vemurafenib and cobimetinib for 48 hours before and after excisional biopsy. This period of interruption may be altered based upon experience in this study.
 
c) If lesion is diagnosed as SCC, treatment may be re-instituted with vemurafenib and cobimetinib at pre-event dose levels after the lesion is excised. If the lesion is not excised, vemurafenib treatment may be resumed if in the investigator’s judgement, the benefit-risk of treatment remains favorable.
 
d) If the lesion is not an SCC, then treatment with vemurafenib and cobimetinib may be restarted at the most recent dose level.

Table 12 Vemurafenib and Cobimetinib Dose Modification Guidelines (Cont.)

Adverse Event	Action

D) Ocular toxicity or visual symptoms Grade ≥ 2
	
a) For any treatment-emergent Grade ≥ 2 visual symptoms or ocular toxicity, cobimetinib and vemurafenib must be interrupted pending diagnostic evaluation, including a complete ophthalmologic examination performed and interpreted by a qualified ophthalmologist, visual acuity testing, intraocular pressure measurements by tonometry, slit-lamp ophthalmoscopy, indirect ophthalmoscopy, and spectral domain optical coherence tomography.
 
b) If RVO is diagnosed, vemurafenib and cobimetinib dosing should be permanently discontinued and the RVO treated per institutional guidelines.
 
c) If RVO is not present, but the visual symptoms are not completely resolved by 28 days, either one or both study treatments may resume if in the investigator's judgement, the benefit-risk of treatment remains favorable.
 
d) If visual symptoms have completely resolved and findings consistent with RVO or neurosensory retinal detachment are not present, the patient may resume use of vemurafenib and cobimetinib with cobimetinib dose reduced by one level (e.g., 80 to 60 mg on a 14/14 day schedule; 60 to 40 mg on a 21/7 or a continuous schedule).
 
e) If ocular toxicity of Grade ≥ 2 recurs a second time, both vemurafenib and cobimetinib should be permanently discontinued.


E) Diarrhea (Grade ≥ 3)
	
a) No change in vemurafenib and cobimetinib dosing will be implemented for Grade 2 diarrhea; patients should receive maximal supportive care per institutional guidelines.
 
b) If Grade ≥ 3 diarrhea occurs despite supportive care, then both drugs should be held until the diarrhea has improved to Grade ≤ 1. If this occurs within 28 days, vemurafenib and cobimetinib may be restarted with cobimetinib dose reduced by one level (e.g., 80 to 60 mg on a 14/14 day schedule; 60 to 40 mg on a 21/7 or a continuous schedule).
 
c) If the diarrhea is not completely resolved by 28 days, then either one or both study treatments may resume if in the investigator's judgement, the benefit-risk of treatment remains favorable.
 
d) If Grade ≥ 3 diarrhea recurs despite supportive care and cobimetinib dose reduction, vemurafenib and cobimetinib should be held until the diarrhea resolves to Grade < 1. If this occurs within 28 days, then therapy may be re-initiated with vemurafenib dose reduced by one level (e.g., 720 to 480 mg). The cobimetinib dose may be maintained at the previously reduced dose.
 
e) If the diarrhea recurs at Grade ≥ 3 despite supportive care and dose reductions in both drugs, then either one or both study treatments may resume if in the investigator's judgement, the benefit-risk of treatment remains favorable.

Table 12 Vemurafenib and Cobimetinib Dose Modification Guidelines (Cont.)

Adverse Event	Action
F) Rhabdomyolysis or symptomatic CPK elevations	
a) Interrupt cobimetinib treatment. If severity is improved by at least on grade within 4 weeks, restart cobimetinib at a dose reduced by 20 mg, if clinically indicated. Vemurafenib dosing can be continued when cobimetinib treatment is modified, if clinically indicated.
 
b) If rhabdomyolysis or symptomatic CPK elevation do not improve within 4 weeks, permanently discontinue cobimetinib treatment.

G) Asymptomatic CPK elevations	
a) Grade ≤ 3: cobimetinib dosing does not need to be modified or interrupted to manage asymptomatic Grade ≤ 3 CPK elevations.
 
b) Grade 4: Interrupt cobimetinib treatment. If improved to Grade ≤ 3 within 4 weeks, restart cobimetinib at a dose reduced by 20 mg, if clinically indicated. Vemurafenib dosing can be continued when cobimetinib treatment is modified, if clinically indicated. If CPK elevations do not improve to Grade ≤ 3 within 4 weeks following dose interruption, permanently discontinue cobimetinib treatment.

H) Liver function test (LFT) elevations	
a) If Grade 1 or 2, continue current dose of vemurafenib and cobimetinib.
 
b) If Grade 3 or 4, hold vemurafenib. Continue current dose of cobimetinib. Upon resolution of LFT to Grade ≤ 1, resume vemurafenib at one lower dose level (e.g., 960 to 720 mg, or 720 to 480 mg).
 
c) If Grade 3 or 4, LFT elevation recurs after one dose reduction, vemurafenib may be reduced by another dose level (e.g., 720 to 480 to 240 mg). Permanently discontinue vemurafenib if Grade 4 LFT elevation recurs when vemurafenib is at a dose of 240 mg bid and continue current dose of cobimetinib.

Table 12 Vemurafenib and Cobimetinib Dose Modification Guidelines (Cont.)

Adverse Event	Action

I) QTc interval prolongation on ECG
	
On-study QTc interval prolongation to >500 ms but <60 ms increment compared with baseline OR prolongation of QTc interval to ≥60 ms compared with baseline (regardless of absolute QTc):
 
a) Rule out other risk factors for arrhythmia (e.g., myocardial ischemia); check for electrolyte disturbances (particularly potassium and magnesium levels) in all cases.
 
b) Evaluate concomitant medications to determine if there is co-administration of drugs that prolongs QTc interval in all cases (e.g., 5-HT₃ receptor antagonist anti-emetics), see Appendix 6.
 
c) Interrupt dosing of vemurafenib and perform ECG and electrolyte monitoring weekly during period of vemurafenib interruption until QTc improves and electrolytes are corrected in all cases; continue dosing with cobimetinib at the current dose if otherwise tolerated.
 
d) If QTc interval does not improve within 28 days after interruption of vemurafenib dosing, permanently discontinue vemurafenib; continue dosing with cobimetinib at the current dose.
 
e) If QTc improves within 28 days, restart dosing of vemurafenib at one reduced dose level (e.g., 960 to 720 mg bid).
 
f) Repeat 12-lead ECG monitoring at Week 2 and Week 4 of the new, lower vemurafenib dose, at Day 1 of each subsequent Cycle×3, and every 3 months thereafter.
 
g) If second increase in QTc interval to >500 ms occurs at the lower dose of vemurafenib, follow Guidelines a through c above, reduce dose of vemurafenib by 1 more dose level (e.g., 720 to 480 mg bid), and follow Guidelines d and e.
 
On-study QTc interval prolongation to >500ms AND >60 ms increment compared with baseline:
 
a) Patient may continue cobimetinib at his/her current dose level. Vemurafenib treatment may resume if in the investigator’s judgement, the benefit-risk of treatment remains favorable.

J) Hemorrhage
	
Grade 3 events: Interrupt cobimetinib treatment. There are no data on the effectiveness of cobimetinib dose modification for hemorrhage events. Clinical judgment should be applied when considering restarting cobimetinib treatment. Vemurafenib dosing can be continued when cobimetinib treatment is interrupted, if clinically indicated.
 
Grade 4 events or cerebral hemorrhage (all grades): Interrupt cobimetinib treatment. Permanently discontinue cobimetinib for hemorrhage events attributed to cobimetinib.

Table 12 Vemurafenib and Cobimetinib Dose Modification Guidelines (Cont.)

Adverse Event	Action
K) Other Grade 4, non-hematologic adverse events related to study drug	
a) Interrupt dosing of vemurafenib and cobimetinib.
 
b) If adverse event resolves to Grade ≤ 1 within 28 days, then (at investigator discretion) restart dosing of vemurafenib and cobimetinib. Both should be decreased by one dose level of the pre-event dose (e.g., 960 to 720 mg for vemurafenib; 80 to 60 mg for cobimetinib on a 14/14 day schedule).
 
c) If the adverse event does not resolve to Grade ≤ 1 within 28 days, discontinue study treatment.
 
d) If the adverse event recurs after 1 dose reduction, either one or both study treatments may resume if in the investigator’s judgement, the benefit-risk of treatment remains favorable.

bid=twice daily; LFT=liver function test; QTc=corrected QT interval; RVO=retinal vein occlusion; SCC=squamous cell carcinoma.

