7.1.1.1 Intensity

Intensity of all adverse events will be graded according to the NCI CTCAE v4.0 on a 5-point scale (Grade 1 to 5) and reported in detail on the eCRF.

Adverse events not listed on the CTCAE should be graded as follows:

CTC Grade ^{a,b}	Equivalent to:	Definition
Grade 1	Mild	Mild; asymptomatic or mild symptoms; clinical or diagnostic observations only; intervention not indicated
Grade 2	Moderate	Moderate; minimal, local or noninvasive intervention indicated; limiting age-appropriate instrumental ADL ^c
Grade 3	Severe	Severe or medically significant but not immediately life-threatening; hospitalization or prolongation of hospitalization indicated; disabling; limiting self care ADL ^d
Grade 4	Life threatening/ disabling	Life-threatening consequences; urgent intervention indicated
Grade 5 ^e	Death	Death related to AE

^a Semi-colon indicates 'or' within the description of the grade; a single dash (-) indicates a grade is not available.

^b Not all grades are appropriate for all AEs. Therefore, some AEs are listed with fewer than five options for grade selection.

^c Instrumental ADL refers to preparing meals, shopping for groceries or clothes, using the telephone, managing money, etc.

^d Self-care ADL refers to bathing, dressing, and undressing, feeding self, using the toilet, taking medications, and not being bedridden.

^e Grade 5 (death) is not appropriate for some AEs and therefore is not an option.

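### Table 12 row E gives two different restart instructions for diarrhea still at Grade 1 on day 28 of a hold, and no clear one for Grade 1 after a recurrence

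*Combined protocol and SAP*

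**What the plan says.** Row E of Table 12, in Section 6.1.1, covers Grade ≥ 3 diarrhea. Three of its items set a recovery criterion.

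- **E(b), Grade ≥ 3 despite supportive care:** "then both drugs should be held until the diarrhea has improved to Grade ≤ 1". The restart rule follows: "If this occurs within 28 days, vemurafenib and cobimetinib may be restarted with cobimetinib dose reduced by one level".
- **E(c), the 28-day rule:** "If the diarrhea is not completely resolved by 28 days, then either one or both study treatments may resume", subject to the investigator judging that benefit-risk remains favorable. No dose reduction is mentioned.
- **E(d), recurrence:** "If Grade ≥ 3 diarrhea recurs despite supportive care and cobimetinib dose reduction", then "vemurafenib and cobimetinib should be held until the diarrhea resolves to Grade < 1". If that level is reached within 28 days, therapy may be re-initiated with vemurafenib one level lower, and cobimetinib may stay at its already reduced dose.

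Item (e) deals with a further Grade ≥ 3 recurrence after both drugs have been reduced. It sets no recovery level.

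Section 7.1.1.1 grades intensity from 1 to 5. The introduction to Section 6.1.1 says that the table does not replace clinical judgement.

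**The concern.** A dose-modification row needs its recovery condition and its non-recovery condition to meet at one boundary, so that each patient state leads to one instruction. In row E they do not meet. Grade 1 counts as recovered in (b) and as not recovered in (c). The two items then differ on which drugs may restart, on whose judgement, and on whether cobimetinib is reduced.

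The recurrence item adds an unexplained change of threshold and has no 28-day fallback of its own.

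Two sites with the same patient could therefore restart different drugs at different doses, each following the table. Section 8.2.4 reports dose interruptions, modifications and their reasons as safety outputs, so differences in reading would also enter the tolerability summaries. Section 3.10.2.3 names diarrhea as the most common adverse event of this combination in the Phase III study, so the row is likely to be used.

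**Working it through.** The plan has no figure to reproduce. The check traces each patient state through the items, taking the 28 days as counted from the start of the hold (the row does not define the start).

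**Step 1: how many levels are there?** On a scale that starts at Grade 1, Grade < 1 means no diarrhea, which in effect is complete resolution. The row has three wordings but two levels: Grade ≤ 1 in (b), and none in (c) and (d).

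**Step 2: trace the states.**

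| State | E(b) | E(c) | E(d) | Outcome |
|---|---|---|---|---|
| First episode, no diarrhea by day 28 | met | not met | not applicable | one instruction |
| First episode, Grade ≥ 2 throughout and at day 28 | not met | met | not applicable | one instruction |
| First episode, Grade 1 reached before day 28 and restarted at once | met | not reached | not applicable | one instruction |
| First episode, Grade 1 and still on hold at day 28 | met | met | not applicable | two different instructions |
| Recurrence after cobimetinib reduction, none within 28 days | not applicable | not met | met | one instruction |
| Recurrence after cobimetinib reduction, Grade 1 persisting past 28 days | not applicable | unclear whether it applies | hold continues, no fallback | no clear instruction |

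The problem is confined to Grade 1 within the first-episode states, in the fourth line. The last line is a gap. It becomes a conflict only if (c) is read to cover recurrences. Item (e) does not fill the gap, because it needs another Grade ≥ 3 recurrence after both drugs have been reduced.

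**Step 3: compare other rows of Table 12.**

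- Row B (photosensitivity) holds until Grade ≤ 1, and its failure rule is "If the photosensitivity does not resolve to Grade ≤ 1 by 28 days".
- Row D (ocular) uses complete resolution of visual symptoms on both sides.
- Row G (asymptomatic Grade 4 CPK) uses Grade ≤ 3 on both sides.
- Row K (other Grade 4 events) uses Grade ≤ 1 on both sides.

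In these four rows the two criteria match. In row E they do not.

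**Step 4: size.** The inputs are the Grade 3–4 diarrhea rate with the combination in the Phase III study, 6.5% (Section 3.10.2.3), and about 130 combination patients (Section 8.3).

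Expected entries to row E = 0.065 × 130 = 8.45, or about 8.

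This assumes that one Phase III rate holds across cohorts that differ in dose and schedule. Those affected are the patients still on hold at Grade 1 on day 28 and those left at Grade 1 after a recurrence. The documents give no rate for either, so at this assumed rate the expected number lies between 0 and about 8.

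**Step 5: DLT evaluability.**

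- The window is the 28 days of Cycle 1 (Section 3.1.3). A hold that begins during Cycle 1 reaches its 28th day at or beyond the end of the window, so the (b)/(c) overlap comes too late to matter.
- Item (d) presupposes a cobimetinib reduction. Under Section 3.1.3, a reduction inside the window already stops the patient counting toward escalation.
- Under Section 3.1.5, related Grade 3 diarrhea not back to Grade ≤ 1 within 7 days is a DLT, and the diarrhea exclusion does not extend to Grade 4. Section 3.1.3 exempts DLT patients from replacement for missed days.

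None of these rules depends on how row E is read.

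**The case against.** The strongest reply is that the overlap is narrow and soft. Under (b) the hold ends when Grade 1 is reached, so a patient who improves early restarts and never meets (c). Both items are permissive, and Section 6.1.1 leaves room for judgement. An investigator who restarts as in (b) also acts within the discretion that (c) allows. This stands as a limit on size. It does not remove the inconsistency: (b) does not oblige a prompt restart, and for a patient still on hold at Grade 1 on day 28 only one of the two items states a dose reduction.

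A second reply is that (b) and (d) do not conflict, because they govern different episodes and a stricter rule on recurrence may be intended. That is correct. A reader might infer that the row contains three mutually contradictory thresholds. The text supports only two levels, one overlap between (b) and (c), and an unexplained change in (d).

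A third reply is that the sign in (d) may be a slip for ≤ or a character lost in conversion. This cannot be excluded, although ≤ appears intact elsewhere in the row. The (b)/(c) overlap does not depend on it.

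**Conclusion.** The inconsistency is real and small. Row E gives two different instructions for diarrhea still at Grade 1 on day 28 of a first hold, and no clear instruction for Grade 1 that persists beyond 28 days after a recurrence. I found nothing elsewhere in the protocol that reconciles the items.

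Two stronger conclusions are tempting and not supported. One is that row E affects who counts for dose escalation. The timing of (c), the reduction that (d) presupposes, and the separate DLT rules for diarrhea rule that out. The other is that about 8 patients would receive conflicting instructions. That figure is the expected number entering the row at an assumed Phase III rate. The affected subset is smaller and the documents do not quantify it.

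The conclusion rests on counting the 28 days from the start of the hold and on taking Grade < 1 to mean no diarrhea.

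**What to change.** The sponsor should reconcile E(b), E(c) and E(d) so that each Grade 1 state falls under one instruction. It should confirm whether the strict inequality in E(d) is intended, and state whether E(c) applies to recurrences as well as to the first episode. The threshold on recurrence need not equal that for the first episode. Which threshold, drug or dose applies is for the sponsor to decide.

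The cost is rewording one row of Table 12. The sample size and the planned analyses do not change.
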